### **3. Materials and methods**

#### *3.1. Participants and Study Design*

This study was planned as a multicenter, randomized, double-blind, and crossover. Approval was obtained from the Erciyes University Clinical Research Ethics Committee for the study (Decision No: 2018/259, Date: 09.05.2018). Twenty healthy adults (10 men, 10 women) between the ages of 19-35, with normal body weight (BMI 18.5-25 kg /m^2) were included in the study. Exclusion criteria were applying an energy-restricted diet in the last three months, having a change in body weight >5 kg in the last three months, having a chronic disease such as diabetes and hypertension, or using a drug that affects the metabolism, having fasting glucose >100 mg/dl, smoking, exercising heavily, having chewing/swallowing difficulties or sensitivity/allergies to any food to be used in the study, vegans, pregnant and lactating women, and skipping breakfast meals. Participants were selected from among Erciyes University students and staff in accordance with the inclusion criteria. Before the participants were included in the study, they were informed about the study in accordance with the Declaration of Helsinki, and volunteers were asked to read and sign the informed consent form.

The physical activity levels of the participants were evaluated simultaneously with dietary assessment by the International Physical Activity Questionnaire (IPAQ) short form at the beginning of the study and on each test day. Their dietary intakes were also assessed by the a-24-hour dietary recall using a photographic atlas of food portion sizes to quantify the data. Diet composition was analysed by the BeBiS Nutrition Information System software version 8.2. Furthermore, body weight and height of participants were obtained at the beginning of the study, and BMI was calculated. Waist and hip circumference were measured using a non-elastic tape with the participants standing, with the face directed towards, shoulders relaxed, and the tape was positioned at a level parallel to the floor. The eating behaviors of all participants were also evaluated using the Dutch Eating Behavior Questionnaire before starting the study. Since the total score obtained from this questionnaire >3.5 is considered as restrictive eating behavior (15), these individuals were not included in the study.

Since individuals were asked to fast for at least 12 hours before consuming the test meals and the postprandial response was more pronounced in the morning, breakfast was chosen as the test meal. On the day before each test meal, the participants were asked to consume their standard dinner at 20:00 and not consume any food or beverage (except water) after dinner, and not to do any physical activity other than their daily routine activities. In addition, test meals were consumed in the follicular phase of the menstrual cycle in order to control the possible effects of the menstrual cycle on appetite for female participants. Similar to previous studies (16,17), days 3-10 after the onset of menses were accepted as the follicular phase.

Participants were served barley bread (BB), oat bread (OB), and wheat breads (WB and WWB) with a standard breakfast on four different days at least two days apart (18). Breads were prepared with similar amounts of energy, protein, fat, carbohydrate, and fiber (except WB). The test meal was served to the participants at 09:00 and they were asked to consume it within 15 minutes. During the test period, participants were not allowed to eat or drink anything other

than water. On the first day of testing, participants were able to consume as much water as they wanted and the amount consumed was recorded. On the other test days, they were asked to consume the amount of water recorded on the first test day. In addition, the participants were allowed to watch movies, read books, play games on electronic devices (computer, cell phone, etc.), and do other sedentary activities during the test days, but they were not allowed to sleep.

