## 4. Statistical Analysis Plan

### 4.1. Sample size

A power-based sample size calculation based on previous research from Bo et al. (25) revealed that 16 participants were needed to provide 80% power to detect 5% difference between groups in primary outcomes. To allow discontinuation during the study, 20 participants (considering 25% losses) were recruited.

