### 4.2. Data analysis

Statistical analysis was performed using the SPSS Statistics (version 22.0) software. Data were expressed as the mean  $\pm$  SD unless otherwise indicated. Normality was assessed using the histogram and normal Q-Q plots, and also Shapiro-Wilk test. Postprandial appetite and glucose responses were quantified as incremental area under the curve (iAUC) calculated according to the trapezoidal rule. One-way analysis of variance (ANOVA) for repeated measures was applied to determine statistical differences between groups. For all statistical analyses, p values less than 0.05 were considered to have statistical significance.

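### The plan states no balance of bread order over the four visits and fits no visit term, so any first-visit effect would add avoidable error to the bread contrasts

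*Combined protocol and SAP*

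**What the plan says.** Section 3.1 gives the design in one sentence: "This study was planned as a multicenter, randomized, double-blind, and crossover". The sample is "Twenty healthy adults (10 men, 10 women) between the ages of 19-35", and the four breads are served "on four different days at least two days apart". No set of orders, Latin square, blocking or other constraint on the list is described.

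The same section runs day 1 differently from the rest. Drinking is unrestricted at that visit, and each person's intake is noted. The rule for the remaining three visits is then: "On the other test days, they were asked to consume the amount of water recorded on the first test day".

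Section 4.2 gives the analysis: "One-way analysis of variance (ANOVA) for repeated measures was applied to determine statistical differences between groups". No visit, sequence or carry-over term is named.

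**The concern.** In a four-period crossover, protection against visit effects comes from the design (each bread equally often at each visit), from the model (visit as a factor), or from both. This plan states neither.

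A first-visit difference is plausible. Drinking is free on day 1 and prescribed afterwards. Day 1 may also be a participant's first use of the appetite scales, the finger-prick series and the buffet, although the documents neither describe nor exclude a familiarisation session.

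If one bread happens to be served first more often than another, part of any first-visit effect enters their contrast. Even when the counts happen to be equal, the visit effect stays in the ANOVA error. Section 4.1 aims at a 5% difference with 16 participants, which leaves little room for avoidable error. With 20 participants and four breads, exact balance is available.

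**Working it through.** **Inputs.** From 3.1: 20 participants (10 men, 10 women), four breads, four days. From 4.1: 16 needed, 20 recruited, 25% losses. From 4.2: one-way repeated-measures ANOVA, 5% level.

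**Assumptions.** The list consists of 20 independent, equally likely orders. The first visit shifts an outcome by δ, in units of the within-person SD σ. Neither is stated in the documents.

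**1. The plan's own figure.** 16 × 1.25 = 20 reproduces the number recruited (25% losses from 20 would leave 15). The 16 cannot be reproduced because no SD is given. For a two-sided paired t test it implies an SD of differences of 5% / 0.749 = 6.7% of the mean.

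**2. Balance of first visits under independent random orders.**
- P(5-5-5-5) = 20! / (5!)⁴ / 4²⁰ = 0.0107.
- Largest minus smallest count (multinomial): 5 or more in 49% of lists, 6 or more in 30%.
- Two given breads: 5 or more apart in 15% (exact 0.154), 6 or more in 8%.
- SD of the count difference for a given pair: √(20 × 0.5) = 3.16.

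**3. Shift in one contrast for one list.** Shift = (count gap / 20) × δ. A gap of 5 gives 0.25δ. The SD over lists is 3.16/20 = 0.16δ.

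**4. Contrast variance without a visit term.** Let I be 1 when a bread is served first. One participant's difference between breads i and j has variance 2σ² + δ² × Var(Iᵢ − Iⱼ). One of the two is first with probability 1/2, so this is 2σ² + 0.5δ². Balanced orders with all 20 completing give 2σ².
- δ = 0.5σ: 2.125/2 = 1.06
- δ = 1σ: 2.5/2 = 1.25
- δ = 2σ: 4/2 = 2.00

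Simulated contrast SEs at 1σ agree: 0.357 for random and 0.320 for Williams orders, and (0.357/0.320)² = 1.24.

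**5. Type I error / power.** Simulation with 20 completers and 3,000 runs per cell. The bread effect was sized for about 80% power at n = 16. The Monte Carlo SE is about 0.004 for a type I error of 0.05.

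| δ | Random, no visit term | Random + visit | Williams, no visit term | Williams + visit |
|---|---|---|---|---|
| 0 | 0.058 / 0.89 | 0.054 / 0.87 | 0.052 / 0.89 | 0.051 / 0.88 |
| 0.5σ | 0.056 / 0.87 | 0.055 / 0.87 | 0.040 / 0.86 | 0.048 / 0.89 |
| 1σ | 0.050 / 0.79 | 0.059 / 0.86 | 0.026 / 0.79 | 0.052 / 0.88 |
| 2σ | 0.051 / 0.58 | 0.051 / 0.87 | 0.002 / 0.49 | 0.055 / 0.88 |

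**6. Why the orders alone are not enough.** A first-visit shift adds δ² × (1 − 1/4) = 0.75δ² to each participant's within-person sum of squares, or 15δ² over 20. With balanced orders none of it enters the bread sum of squares. Without a visit term it all goes to error: 15/57 = 0.26, so at δ = 1σ the expected error mean square is about 1.26σ². The contrast is estimated more precisely, but the test is conservative and gains no power.

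**7. What balance adds once visit is fitted.** Random orders still raise contrast variance by about 5.6% on average and by 9.5% or more in one list in ten. 20 × 0.056 = 1.1, so about one participant.

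**8. Losses.** With four random losses from the Williams orders, the count difference for a pair has SD √(4 × 0.5 × 16/19) = 1.3. For 16 random orders it is √(16 × 0.5) = 2.8. At δ = 1σ with 16 completers, power under Williams orders is 0.78 with a visit term and 0.68 without.

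**The case against.** **Silence is not evidence of imbalance.** A reader might infer that bread order was left unconstrained. The documents do not say so. The word used in 3.1 fits a balanced list as well as an unbalanced one, and the counts in the working hold only for independent orders. This stands: the supportable statement is that no balance is stated. Much of the text is in the past tense, so the list may already exist.

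**No systematic bias.** A reader might infer that the ANOVA will mistake a first-visit shift for a bread effect. Averaged over random orders, type I error stays near 0.05 even at 2σ. In a single list it can go either way: simulated at 1σ and 2σ, it is 0.067 and 0.089 for first-visit counts 9, 2, 5, 4, but 0.045 and 0.030 for counts 8, 3, 5, 4. The loss is of precision.

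**The first-visit effect is not shown.** The water rule asks for the day 1 amount on later days, so amount is meant to be matched within person and only free versus prescribed drinking differs. This stands. With no visit effect, the planned analysis loses nothing.

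**The worst pair exaggerates.** The 49% is for the most unequal of six pairs, and a given pair reaches that gap in 15% of lists. Both figures belong in the account.

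**Carry-over.** It is tempting to say that Williams orders also protect against carry-over across the two-day minimum gap. They do not protect an unadjusted contrast. No bread follows itself, so the mean for bread i carries a quarter of the summed carry-over c of the other three, and the contrast of i against k is biased by (c_k − c_i)/4. The documents describe no carry-over mechanism, and none is claimed here.

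**Conclusion.** The concern holds as a minor design improvement. As written, the plan secures no balance of breads over visits and does not adjust for visit. Under independent random orders and an assumed first-visit effect of 1 within-person SD, the planned analysis carries about 25% more contrast variance than balanced orders would, and power is 0.79 against 0.88 with Williams orders and a visit term. At 0.5 SD the excess variance is about 6%, and at zero there is none.

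Most of the power is recovered by the visit term, and balance adds roughly one participant's worth of information. Balanced orders without a visit term would not raise power. The result rests on the assumed list method and effect size, and it does not show that the trial's actual list was unbalanced.

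**What to change.** - **Section 3.1:** state that participants are allocated at random to the four orders of a Williams square, five per order, with any replacement made within the same order. Each bread then falls five times at each visit. Ten of each sex cannot be split equally over four orders, but men 2-2-3-3 and women 3-3-2-2 give five per order.
- **Section 4.2:** add visit as a factor to the repeated-measures model.
- **If allocation is already done:** describe the list actually used, balanced or not, and add the visit term in either case.

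**Cost:** about two sentences and a different list, with no extra participants, visits or measurements. The visit term uses 3 of the (20 − 1) × (4 − 1) = 57 error degrees of freedom, leaving 54. Balance is exact only if all 20 complete, and is approximate after losses.

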## 2. Objective

This study aimed to compare the postprandial effects of  $\beta$ -glucan on glycemia and appetite of breads derived from oats and barley, which are the best natural grain sources. In addition, the positive health effects of  $\beta$ -glucan were sought to be determined independent of total dietary fiber intake, using not only WB as the control food but also WWB, which has a dietary fiber content equal to that of breads containing  $\beta$ -glucan.

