### 3.2. Chemical Analysis

In this research, total fat, protein,  $\beta$ -glucan, total available carbohydrate, and total dietary fiber analyzes were performed chemically in the flour and bread samples. Chemical analyzes were performed in parallel and in duplicate. Data were reported on dry matter and average values of at least two analyzes were taken. The energy value (kcal) per test portion was calculated using the weight (g) of each test portion and the formula  $[(4 \times \text{protein}) + (9 \times \text{fat}) + (4 \times \text{available carbohydrate})]$  (19). All chemical analyzes were conducted in Erciyes University Veterinary Faculty Food Hygiene and Technology Laboratory.

All chemical analysis was performed as described above by taking a sample of several flours commonly available in Turkey. Among these flours, barley and oat flours with the highest  $\beta$ -glucan content were selected for baking bread as well as white flour and whole wheat flour having the most similar macronutrient content with barley and oat flours. A preliminary study was conducted to evaluate  $\beta$ -glucan content and bread baking tests were applied. For BB and OB, the content of  $\beta$ -glucan was targeted to be about 3 g in one serving. WB and WWB were used as reference and control foods, respectively. After the test breads were prepared, all the chemical analyzes described above were carried out again and the nutritional composition of the breads was found as in Table 1.

**Table 1.** Energy and macronutrient contents of test breads

	White bread	Whole-wheat bread	Barley bread	Oat bread
Portion size (g)	72	73	73	70
Energy (kcal)	150	147	154	133
Carbohydrate (g)	28.7	27.3	28.9	23.9
Protein (g)	5.0	5.7	4.9	4.7
Fat (g)	1.7	1.7	2.1	2.0
Dietary fiber (g)	2.2	6.8	6.9	9.0
$\beta$ -glucan (g)	1.2	1.4	3.1	3.2

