### 3.4. Test meals

The foods and nutritional composition of the test breakfast meals are as in Table 2.

**Table 2.** Nutritional composition of the component foods in test meals

Foods	Portion size (g)	Energy (kcal)	Carbohydrate (g)	Protein (g)	Fat (g)
Feta cheese	15	34.8	0.66	1.8	2.7
Cheddar cheese	24	79.2	0.48	5.28	6.24
Olive	24	57.1	0.30	0.32	4.79
Honey	20	64	16.6	0.06	-
Black tea	150 ml	-	-	-	-

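### Oat bread is not matched to the other breads on available carbohydrate, although section 3.1 says it is, so unadjusted oat glucose contrasts partly reflect a smaller carbohydrate load

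*Combined protocol and SAP*

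**What the plan says.** Section 3.1 describes the four breads as matched: "Breads were prepared with similar amounts of energy, protein, fat, carbohydrate, and fiber (except WB". However the exception for white bread is read (fibre only, or all nutrients), it does not extend to oat bread.

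Table 1 in section 3.2, headed "Energy and macronutrient contents of test breads", gives the measured values in the order white, whole-wheat, barley, oat: "Carbohydrate (g) 28.7 27.3 28.9 23.9", "Energy (kcal) 150 147 154 133" and "Dietary fiber (g) 2.2 6.8 6.9 9.0". Section 3.2 also says that "total available carbohydrate, and total dietary fiber analyzes were performed chemically in the flour and bread samples", and it computes energy from protein, fat and available carbohydrate.

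Table 2 in section 3.4, "Nutritional composition of the component foods in test meals", lists the foods served with every bread. Section 2 sets out to compare effects "on glycemia and appetite of breads derived from oats and barley", with white and whole-wheat bread as controls. Section 4.2 reduces postprandial glucose to iAUC and compares breads by one-way repeated-measures ANOVA. It contains no adjustment or standardisation for carbohydrate.

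**The concern.** Glucose iAUC depends on how much available carbohydrate is eaten as well as on the food that carries it. If one bread delivers less, a lower iAUC for that bread mixes the property under study with a smaller load. A crossover design does not remove this, because the lower carbohydrate comes with the oat bread every time it is served. The distortion has one direction and does not shrink as participants are added.

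Attribution is at stake. Oat and barley bread have nearly the same beta-glucan (3.2 g and 3.1 g), so a raw glucose difference between them could be read as one grain being better than the other. Against white or whole-wheat bread, a raw difference could be read as a beta-glucan effect. A reader told that carbohydrate was similar would have no reason to doubt either reading.

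**Working it through.** **Inputs.** Table 1: carbohydrate, protein, fat, fibre and energy per bread portion. Table 2: carbohydrate in the other foods.

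**Step 1: are the Table 1 figures available carbohydrate?** Apply the plan's formula, 4 × protein + 9 × fat + 4 × carbohydrate:

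- White: 20.0 + 15.3 + 114.8 = 150.1 kcal (stated 150)
- Whole-wheat: 22.8 + 15.3 + 109.2 = 147.3 kcal (stated 147)
- Barley: 19.6 + 18.9 + 115.6 = 154.1 kcal (stated 154)
- Oat: 18.8 + 18.0 + 95.6 = 132.4 kcal (stated 133)

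All agree within the rounding of the inputs. Subtracting fibre from carbohydrate first gives about 141, 120, 127 and 96 kcal, which does not fit. The figures are therefore available carbohydrate, and the gap is not an artefact of counting fibre differently.

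**Step 2: carbohydrate from the rest of the breakfast.** 0.66 + 0.48 + 0.30 + 16.6 = 18.04 g, the same at all four meals.

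**Step 3: shortfall of oat.** Shortfall = (comparator − oat) / comparator, for the bread alone and for the whole meal. The oat meal has 23.9 + 18.04 = 41.94 g.

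| Comparator | Bread (g) | Shortfall, bread alone | Meal (g) | Shortfall, whole meal | Meal ratio to oat |
|---|---|---|---|---|---|
| Barley | 28.9 | 5.0/28.9 = 17.3% | 46.94 | 5.0/46.94 = 10.7% | 46.94/41.94 = 1.12 |
| White | 28.7 | 4.8/28.7 = 16.7% | 46.74 | 4.8/46.74 = 10.3% | 46.74/41.94 = 1.11 |
| Whole-wheat | 27.3 | 3.4/27.3 = 12.5% | 45.34 | 3.4/45.34 = 7.5% | 45.34/41.94 = 1.08 |

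The other three breads lie within (28.9 − 27.3)/28.9 = 5.5% of each other, so oat is the outlier. Barley and white meals are practically equal (46.9 and 46.7 g).

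**Step 4: what this could do to glucose iAUC.** The documents give no relation between iAUC and carbohydrate, so this step is an assumption shown as a range. With no true difference between breads:

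- Fully proportional: oat lower by 10.7% (barley), 10.3% (white), 7.5% (whole-wheat).
- Half proportional: 5.3%, 5.1% and 3.7%.
- No response to a difference of this size: 0%.

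**Step 5: energy and fibre.** Oat bread has (154 − 133)/154 = 13.6% less energy than barley. Its fibre is 9.0/6.9 = 1.30 times barley's and 9.0/6.8 = 1.32 times whole-wheat's. The statement in section 3.1 therefore fails for oat bread on energy and fibre too.

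**The case against.** The best defence is that this is a whole-food comparison. Section 3.2 aims at about 3 g beta-glucan per serving of barley and oat bread, section 3.3 uses 100% flour of each grain, and section 1 asks about natural sources. With these flours, beta-glucan and carbohydrate cannot both be matched: at barley's 28.9 g carbohydrate, oat bread would carry 3.2 × 28.9/23.9 = 3.9 g beta-glucan. Lower carbohydrate is partly what oat bread is, and Table 1 discloses it. This stands as a reason to keep the raw comparison. It does not make the word similar correct, and it does not support attributing a raw difference to beta-glucan or grain alone.

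A second objection concerns scaling. Dividing by grams assumes full proportionality and gives the 16.6 g from honey the same weight as bread carbohydrate, so it could hide a true oat effect. It also leaves the fibre difference in place. This stands too, and it is why the scaled analysis should support the raw one and not decide the conclusion.

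Three stronger readings are tempting, but the documents do not support them.

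- *The gap is about twice the effect the trial was powered for.* The 5% in section 4.1 refers to primary outcomes that are not named, and it is on the outcome scale. Setting it against a percentage of carbohydrate needs glucose iAUC to be one of those outcomes and to respond in proportion.
- *Oat versus barley is the first objective, and it is confounded.* Section 2 can be read that way, but section 1 describes judging the beta-glucan breads against white and whole-wheat bread. The mismatch affects oat on either reading.
- *Lower glucose after oat bread would be simply a carbohydrate effect.* Oat bread also has more fibre, so carbohydrate is one candidate explanation among several.

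**Conclusion.** The point holds. Section 3.1 and Table 1 disagree about oat bread, and the analysis plan has no step that deals with the consequence. All three oat glucose contrasts are affected, including the one against whole-wheat bread, which section 3.2 names as the control food. Barley versus white is matched.

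The carbohydrate shortfalls are arithmetic on Tables 1 and 2. Rounding in Table 1 moves the oat-barley meal figure only between 4.9/46.89 = 10.45% and 5.1/46.99 = 10.85%. Assay error is not included, because Table 1 gives averages without a measure of spread. The possible effect on iAUC is much less certain. Against barley it runs from nothing to 10.7%, the top of the range resting on the assumption that iAUC responds no more steeply than in proportion to meal carbohydrate. The raw contrast remains valid as a comparison of portions as served, so the trial is not undermined. The limit is on what a lower oat glucose response can be attributed to.

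**What to change.** 1. **Section 3.1.** Replace the matching statement with one that agrees with Table 1: oat bread is not matched on available carbohydrate (23.9 g against 27.3 to 28.9 g), nor on energy or fibre.
2. **Section 4.2.** Add a supporting sensitivity analysis of glucose iAUC divided by meal available carbohydrate (46.74, 45.34, 46.94 and 41.94 g for white, whole-wheat, barley and oat), covering all oat contrasts. In each pair this is equivalent to multiplying oat iAUC by about 1.12 against barley, 1.11 against white and 1.08 against whole-wheat. The document is written in the past tense, so label the analysis post hoc if the data are already collected.
3. **Reporting.** Show the scaled result beside the raw one, without making either a condition for the other. Describe raw oat differences as effects of the portion as served. If they shrink materially under scaling, do not attribute them to beta-glucan or grain source alone. State what counts as material before the scaled analysis is run.

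The cost is one corrected sentence and one extra analysis of measurements the trial already makes; no new participants, visits or breads are needed. The downside is that proportional scaling may over-correct and does not remove oat bread's higher fibre (9.0 g against 6.9 g barley and 6.8 g whole-wheat). Both limits should be stated with the result.

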## 1. Background

The prevalence of overweight and obesity worldwide increases significantly with concomitant diseases. Disruption of energy balance is known as the main cause of obesity. To maintain energy balance, weight control (dietary intervention, physical activity, behavioral therapy) results in short-term weight loss, but sustained weight maintenance is difficult. So alternative weight-loss strategies can be a solution (1). Epidemiological studies show that high dietary fiber intake is associated with lower body weight and waist circumference (2,3). The controlled intervention studies report that weight gain can be prevented by reducing appetite and energy intake with high dietary fiber intake (4–7). In addition, most studies show that high fiber intake is also associated with improved postprandial glycemic response (8). These potential beneficial effects of dietary fiber, which is divided into two as soluble and insoluble according to its physiological effects, can be attributed to  $\beta$ -glucan, a type of soluble fiber (9). However, results from studies examining the effects of  $\beta$ -glucan on appetite are not consistent and the underlying mechanisms are not yet clear. It is thought to contribute to a feeling of satiety by increasing the duration of oral exposure to food and abdominal distension and by increasing short-chain fatty acid production as a result of colonic fermentation (10–12). The hypothesis that  $\beta$ -glucan affects appetite by acting on gastrointestinal hormones is still controversial (13). On the other hand, the blood-glucose-lowering properties of  $\beta$ -glucan derived from oats and barley have been confirmed by the European Food Safety Authority (EFSA), with a health claim that 4 g  $\beta$ -glucan can be used per 30 g of available carbohydrates per meal (14). The lowering effects of  $\beta$ -glucan on blood glucose and insulin levels and blood pressure are speculated to be due to its prebiotic properties and its effects on weight loss (9).

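### Water volume is matched to visit 1 but drinking times are neither recorded nor matched, which adds avoidable noise of unknown size to late appetite ratings and lunch intake

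*Combined protocol and SAP*

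**What the plan says.** Section 3.1 sets the water rule in two sentences. For visit 1: "On the first day of testing, participants were able to consume as much water as they wanted and the amount consumed was recorded". For visits 2 to 4: "On the other test days, they were asked to consume the amount of water recorded on the first test day". Water is the only intake permitted between breakfast and lunch.

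Section 3.5 has appetite rated before breakfast and then at 15, 30, 60, 90, 120, 150 and 180 minutes. Section 3.6 places the buffet lunch at three hours, directly after the last rating. Section 4.2 summarises appetite as a trapezoidal incremental area (iAUC) and compares breads by a one-way repeated-measures ANOVA, with no term for visit.

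No section says when the water is to be drunk, whether visit-1 drinking times are noted, whether drinking stops before the last rating or lunch, or whether the amount taken at visits 2 to 4 is checked. Section 3.1 describes a randomised crossover but gives no sequence scheme.

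**The concern.** By matching volume, the authors treat water as something that could disturb the comparison. The Background gives a reason why timing would matter too: β-glucan is thought to "contribute to a feeling of satiety by increasing the duration of oral exposure to food and abdominal distension". That sentence is about β-glucan, not water, so extending it to a drink is an inference, though a natural one. How much water is in the stomach at a rating depends on when it was drunk as well as on the day's total.

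The rule also differs between visits. At visit 1 any late drinking follows thirst. At visits 2 to 4 a participant who is short of the target has an added reason to drink late, close to the last ratings and lunch. At stake is the precision of appetite iAUC and lunch intake, in a trial whose sample size leaves little room for extra within-person variation.

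**Working it through.** **Inputs from the documents**
- Rating times 0, 15, 30, 60, 90, 120, 150, 180 min (Section 3.5); trapezoidal iAUC (Section 4.2).
- Sample size (Section 4.1): "16 participants were needed to provide 80% power to detect 5% difference between groups in primary outcomes", and "20 participants (considering 25% losses) were recruited".
- Significance (Section 4.2): "p values less than 0.05 were considered to have statistical significance". I take this as two-sided.
- Not given: primary outcome, scale of the 5%, SD, test used for the calculation, and any effect of water on appetite or intake.

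**1. The plan's own figure.** The 16 cannot be reproduced, because Section 4.1 offers only "A power-based sample size calculation based on previous research" and no SD. It can be inverted. For a paired t test, power comes from the noncentral t with n − 1 degrees of freedom and noncentrality 5√n / SD, with SD in percent of the mean. Setting n = 16 and power 80% gives an SD of the paired difference of 6.67%. The normal approximation gives 5 × 4 / (1.96 + 0.84) = 7.1%. The step to 20 is 16 × 1.25.

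**2. Weight of the late ratings.** Each rating's trapezoid weight is half the sum of its neighbouring intervals: 7.5, 15, 22.5, 30, 30, 30, 30, 15 min, total 180. The 150-minute rating carries 30/180 = 16.7% and the 180-minute rating 15/180 = 8.3%; together 45/180 = 25%. This assumes a net incremental area; the plan does not say how time on the far side of baseline is handled.

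A 5% change in the area therefore needs a shift of 5/25 = 20% of the mean incremental height at both late ratings, or 5/8.33 = 60% at the 180-minute rating alone. Lunch intake is one number and has no such dilution, so it is the more exposed outcome.

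**3. Timing as random noise (assumed sizes).** If timing adds independent noise with SD τ (percent of the mean) at each visit, the SD of a paired difference becomes √(6.67² + 2τ²).

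| τ | SD of difference | Power, n = 16 | Power, n = 20 |
|---|---|---|---|
| 0 | 6.67 | 80% | about 89% |
| 1 | 6.82 | 78% | 88% |
| 2 | 7.25 | 73% | 83% |
| 3 | 7.91 | 66% | 77% |
| 5 | 9.72 | 49% | 59% |

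The documents do not say which τ applies. If the cited earlier study had similar water noise, part of this is already in its SD.

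**4. Visit 1 against visits 2 to 4.** Suppose visits 2 to 4 share a water effect s that visit 1 lacks. The contrast of breads A and B then shifts by s × (difference between the numbers who had A and B at visit 1) / 20.
- Balanced order (5 participants per bread at visit 1): shift = 0.
- Simple randomisation: the difference in counts has variance 20 × (1/4 + 1/4) = 10, so the shift has mean 0 and SD √10/20 × s = 0.16 s. By simulation, the 95th percentile of its absolute value is 0.30 s.
- A 5% shift in a bread contrast would need s of about 5/0.158 = 32% at one SD, or 5/0.30 = 17% at the 95th percentile.

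**The case against.** Matching each person to their own volume is a deliberate within-person control, and if followed it keeps the total constant across breads. Nothing in the documents says that anyone falls short of the target or drinks late. The lunch itself offers water, juice and a yogurt drink, which a timing rule leaves untouched. All of this stands. It limits the size of the problem, but it does not supply the missing control of timing.

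Three stronger readings are tempting and are not supported.

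- A reader might infer that late drinking can move the results by as much as the 5% sought. No water effect is given, and the 5% has no stated outcome or scale. Assume 5 to 10 composite points at both late ratings: one person's area moves by 5 × 45 = 225 to 10 × 45 = 450 point·min. Assume a mean change of 20 to 30 points: 5% is 0.05 × 180 × 20 = 180 to 0.05 × 180 × 30 = 270 point·min. These look alike, but the first is one person at one visit and the second is a difference between bread means. Averaged over 20 people, one late drink moves a bread mean by 11 to 23 point·min, or 0.04 to 0.13 of that target. For lunch there is no figure at all.
- A reader might infer that the visit-1 rule biases the bread comparison. It is a period effect, with expected value zero under randomised order. Even if everyone drank late at all of visits 2 to 4, with the same assumed 225 to 450, simple randomisation gives a shift of 36 to 72 point·min at one SD (0.13 to 0.40 of the target) and 68 to 135 at the 95th percentile (0.25 to 0.75).
- A reader might infer that late drinking cannot occur at visit 1. It can, since drinking there is free. Only catch-up driven by a target is absent.

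**Conclusion.** The gap is real and minor. Volume is matched, timing is neither recorded nor matched, and the target applies only at visits 2 to 4. This allows avoidable within-person noise in the late appetite ratings, which carry 25% of the trapezoid weight, and in lunch intake, which is not diluted.

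The size is unknown. The power figures rest on an SD inferred from the stated 16 and on assumed noise, so they show sensitivity and are not estimates. Bias in a bread contrast would require either unbalanced bread order at visit 1, which cannot be checked because no sequence scheme is given, or drinking times that depend on the bread, for which the documents give no evidence.

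**What to change.** At visit 1, record the time as well as the amount of each drink. At visits 2 to 4, have the participant repeat both, and note any departures. This keeps the authors' own-volume principle and leaves visit-1 drinking free. The cost is a little more recording and slightly less freedom for participants at visits 2 to 4. A fixed volume at fixed times for everyone would also standardise timing, but it imposes drinking at every visit and is more open to debate.

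The protocol is written in the past tense, so visits may already be complete. In that case:
- include visit (period) with bread in the repeated-measures model; with 20 complete participants this costs 3 of the (20 − 1) × (4 − 1) = 57 error degrees of freedom;
- report how many participants had each bread at visit 1;
- state unrecorded water timing as a limitation.

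A visit term removes an average difference between visit 1 and the later visits. It cannot remove the person-to-person noise from drinking at different times.
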